APPENDIX A - TIME AND EVENTS SCHEDULE

Period		Enrollment (Baseline) Visit	Day 3 Phone Call	Day 15 Visit	Day 30 Visit	Day 45 Visit	Day 61 Visit	Day 75 Visit	Day 91 Visit	Day 105 Visit	Day 121 Visit
Study Day	-14 - 0	0	3 (+2)	15 (+3)	30 (+3)	45 (+3)	61 (+3)	75 (+3)	91 (+3)	105 (+3)	121 (+3)
Informed Consent	Х										
Demographic Information	Х										
Medical/Surgical History/Physical Exam	Х										
Inclusion/Exclusion Criteria	Х	X^1									
Baseline Health Economics		Х									
Pain Score Assessment (NPRS)	Х	Х					Х	X ¹⁴	X^4		
Michigan Neuropathy Screening Instrument	Х										
Pain Phase Assessment	X										
Urine Drug Screen	Х										
Urine Pregnancy Test	X ²										
Height and Weight	Х										X ⁷
Measurement of Foot Thickness	Х										
Obtain Ankle-Brachial Index (ABI) & Assess Venous Insufficiency	Х										X ³
Vibration Perception Threshold (VPT)		Х		Х	Х	Х	Х	Х	Х	Х	Х
Quantitative Sensory Test (QST)		Х		Х	Х	Х	Х	Х	Х	Х	Х
Sural Nerve Conduction Velocity (NCV)		Х									Х
Measure Blood Glucose		Х			Х		Х		Х		Х
Measure HbA1c	Х										Х
Brief Pain Inventory (BPI)		Х			Х		Х		Х		Х
Skin Perfusion Pressure (SPP)		Х					Х				Х
Brief Fatigue Inventory (BFI)		Х			Х		Х		Х		Х
Hospital Anxiety and Depression Scale (HADS)		Х			Х		Х		Х		Х
NeuroQoL		Х									Х
Dispense Active Study Device		Х									
Study Device Training		Х							10		
Randomize and Dispense Study Device							X ⁵	X9	X ¹⁰		
Distribute Diary (NPRS, PGIC) ⁶		X		Х	Х	Х	Х	Х	X ¹¹	Х	
Collect Diary				Х	Х	Х	Х	Х	Х	Х	Х
Study Device Blinding Assessment							-				Х
Response Assessment							X ⁵	X^{14}	X ⁴		
Assess Adverse Events	X ⁸	Х	Х	Х	Х	Х	Х	Х	Х	Х	Х
Assess Concomitant Medications	Х	Х	Х	Х	Х	Х	Х	Х	Х	Х	Х
Assess Subject Adherence to Treatment			Х	Х	Х	Х	Х	Х	Х	Х	Х
Treatment Satisfaction				X	X	Х	X	X	X	Х	Х
Return Study Device and Unused DACs									X ¹³		Х
3mm Skin Punch Biopsy at distal leg and distal thigh		X ¹²									X ¹²

1. The Screening Visit and the Enrollment Visit may occur on the same day in which I/E criteria will not need to be reviewed.

- 2. Urine pregnancy test will be performed on women of child-bearing potential.
- 3. ABI and Venous Insufficiency will be obtained at Day 121 for those subjects who were responders completing treatment through Day 120.
- 4. Only subjects determined to be non-responders at Day 75 will be assessed. Subjects determined to be non-responders at Day 91 will be terminated from the study.
- 5. Non-responders at Day 61 will continue treating with the Active device. Response will again be assessed at Day 75.
- 6. Numeric pain scores along with weekly PGIC will be recorded by the subject on the diary each day immediately after the morning treatment.
- 7. Collect only weight at end of study visit.
- 8. Assessment of adverse events will be conducted after the signing of the Informed Consent.
- 9. Subjects determined to be responders at Day 75 will be randomized to active or sham and continue treating through Day 120.
- 10. Subjects determined to be responders at Day 91 will be randomized to active or sham and continue treating through Day 120.
- 11. A new diary is dispensed only to subjects who are responders.
- 12. A 3mm skin punch biopsy will be obtained from at least 2 subjects in each pain phase category at the Enrollment Visit and at Day 121.
- 13. Only subjects determined to be non-responders will return their study devices and unused DACs at Day 91.
- 14. Only subjects determined to be non-responders at Day 61 will be assessed. Non-responders at Day 75 will continue treating with the Active device. Response will again be assessed at Day 91.

Phasing of Neuropathy

APPENDIX C – SUBJECT DIARY FOR DAILY PAIN SCORE AND WEEKLY GLOBAL IMPRESSION OF CHANGE

PATIENT: _____ Week Start Date: _____

Treat Both Feet, Simultaneously, Twice Daily for 30 minutes, 8am +/- 2 hours and 8pm +/- 2hours.

Circle the Pain Score which represents your average Pain over the last 24 hours after completing your Morning (am) treatment.

On the scale below, a score of 0 represents No Pain whereas a score of 10 represents the Worst Possible Pain. Every 7 days, mark your overall status compared to the start of the study.

			0	l 2 Mild	3	4 5 Mode	6 rate	7 8	3 9 Severe	10		
		No Pain										Worst Possible Pain
Date:		0	1	2	3	4	5	6	7	8	9	10
Date:		0	1	2	3	4	5	6	7	8	9	10
Date:		0	1	2	3	4	5	6	7	8	9	10
Date:		0	1	2	3	4	5	6	7	8	9	10
Date:		0	1	2	3	4	5	6	7	8	9	10
Date:		0	1	2	3	4	5	6	7	8	9	10
Date:		0	1	2	3	4	5	6	7	8	9	10
	Since the start (check one bo	t of the	study,	my ove	rall sta	tus is:						
	Very Muc	h Wors	e	Muc	h Wor	se [Mini	mally V	Vorse	  1	lo Chai	nge
	🗌 Mi	nimall	y Impro	oved	🗌 Mu	ich Imp	roved		Very M	uch Imp	proved	

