Endpoints	For this proof of concept study, the primary endpoints will be changes in Vibration Perception Threshold and Quantitative Sensory Testing between baseline and end of treatment. Secondary endpoints will be changes in nerve conduction velocity (NCV) of the sural nerve and amplitude from baseline to end of treatment, changes in Skin Perfusion Pressure (SPP) from baseline to end of treatment, change in Pain Intensity using the 11-point Numeric Pain Rating Scale (NPRS) from baseline to end of treatment, change from baseline in Brief Pain Inventory (BPI) and Brief Fatigue Inventory (BFI), change from baseline in Patient Global Impression of Change (PGIC), change from baseline in Hospital Anxiety and Depression Scale (HADS), and changes from baseline in neuropathy and foot ulcer specific quality of life instrument (NeuroQoL).
	Safety will be assessed through review of Adverse Event (AE) reports and concomitant treatments and medications. All concomitant drug or non-drug treatments used during the study will be recorded. Safety outcomes will be assessed at the interim visits and the end of study visit.
Study Procedures	Following informed consent and assessment of eligibility, subjects will complete Section A-History of the Michigan Neuropathy Screening Instrument (MNSI) with Section B- Physical Assessment completed by the site. A measurement of the depth of the right foot will be measured from the most inferior aspect of the medial malleolus to the plantar aspect of the foot when residing on the treatment pad. The depth should not be more than 8cm for eligibility. A finger stick will be performed on the subject to obtain a baseline HbA1c value (A1C Now [®] test kit) and subjects will complete a Urine Drug Screen in office. Subjects will undergo the Ankle-Brachial Index (ABI), Venous Insufficiency Assessment, and Pain Phase evaluation (at least 10 subjects in each of the 2, 3, and 4 pain phases will be enrolled). For subjects of child bearing potential a urine pregnancy test will be obtained.

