The label on each study device kit will contain the protocol number and kit number. There will be sufficient space for study personnel to write the subject number, date dispensed, and the initials of the dispenser on the distribution label.

J. Preparation and Administration

Each subject will receive two devices to use during the study. Each treatment session with the study devices will be 30 minutes in duration. All treatment sessions will be self-administered by the subject or his/her family or caregiver in the home or similar setting.

The first treatment with the study devices will be administered on the morning of the day following the Enrollment Visit (Day 1) at 8am (\pm 2 hours). Subjects will assume a comfortable position and place their feet (both feet will be treated) on the treatment applicators of the PEMF devices, centering the applicators under the plantar surface (bottom of foot) of each foot as identified by the investigator. Treatment will be administered continuously for 30 minutes on both feet simultaneously. Thereafter, subjects will self-administer treatments twice daily, at 8am (\pm 2 hours) and 8pm (\pm 2 hours) up to Day 120 (Day 91 for non-responders).

Prior to initiation of each treatment session, the subject will take the treatment applicator of each study device and insert it into a new Disposable Applicator Cover. When inserted properly, the yellow starburst logo on the treatment applicator is aligned with the same logo on the Disposable Applicator Cover, and the words "This side towards patient" will be visible through the clear window of the Disposable Applicator Cover. When applied to the subject's feet, the side of the treatment applicator with the yellow starburst logo is directed toward the bottom of the foot (plantar surface). Further directions for use for the PEMF system are found in the Instruction Manual. Upon completion of the treatment session, the subject will remove and discard the Disposable Applicator Covers, and store the PEMF devices until the time of the next scheduled treatment session. Disposable Applicator Covers may be discarded as standard waste.

K. Blinding

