pressure in the angiosome is made. SPP (mmHg) at reactive hyperemia is recorded. A second measure of SPP will be obtained on the plantar aspect of the right foot directly below the location where the SPP was performed on the dorsal aspect of the right foot. SPP will be conducted at the Enrollment Visit, Day 61, and end of study visit (Day 121). An increase in SPP would be considered clinically meaningful.

Pain Intensity (PI): a validated 11-point Numeric Pain Rating Scale (NPRS) with scores (0-10) collected as patient-reported outcomes on a paper diary, at Screening for eligibility, at the Enrollment Visit for a baseline value, and Days 61, 75 and 91 to assess response (1-point decrease from baseline in average pain score over the last 24 hours). On the diary, PI will be assessed after each morning ($8am \pm 2$ hours) treatment. Subjects will report their average pain score over the last 24 hours. Diaries will be distributed and collected from the subjects every 2 weeks to ensure compliance.

Brief Pain Inventory (BPI): is a 32-question long form questionnaire that assesses the severity of pain and its impact on specific daily functions. Cronbach's alpha reliability ranges from 0.77-0.91. The BPI long form will be administered at the Enrollment Visit, Day 30, 61, 91, and end of study visit (Day 121). The change from baseline will be captured and assessed.

Brief Fatigue Inventory (BFI): is a 4-question assessment that assesses the level of fatigue and the impact of the fatigue on daily function over the last 24 hours. A global fatigue score is collected by averaging all items on the BFI. Cronbach's alpha reliability ranges from 0.82-0.97. BFI is patient reported and collected at the Enrollment Visit, Days 30, 61, 91, and end of study visit (Day 121). The change from baseline will be captured and assessed.

Patient Global Impression of Change (PGIC): a 7-point validated categorical scale of overall change in status since initiation of treatment with the study device. PGIC allows subjects to integrate into one overall evaluation of the different aspects of their response to treatment, including pain reduction, improvement in functioning and side effects. PGIC will be collected every 7 days in the paper diary, immediately following the morning treatment. PGIC serves to anchor within-subject changes in pain over the course of treatment.

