Randomization of subjects can occur at different times, depending on when the subject is determined to be a responder. Once a subject is determined to be a responder (based upon a 1-point decrease in average pain score over the last 24 hours using the NPRS), the subject will return the active devices and be randomized 1:1 to receive active treatment or inactive sham devices and be instructed to treat through study day 120. If a subject is determined to not be a responder at Day 91, i.e., their final chance to be randomized, the subject will be terminated from the study at the end of the Day 91 visit.

C. Summarization of Results

The tabulations will be based on the paired results for the change from the baseline to study day 120 for patients who are randomized, and separately for the last observation. Supportive subject data listings will be sorted and presented by subject number, visit date and relative study day. Listings will also include the number of days relative to the initiation of treatment. Two sets of analyses will be generated; summary tabulations for all randomized subjects who complete the baseline and study day 120 evaluations (*Completers Analysis Set*), and all randomized subjects using the baseline and last recorded set of evaluations (*End of Study Evaluation Set*). This latter set should include all subjects who were randomized and complete at least one set of evaluations after randomization.

Specific algorithms will be described in the Statistical Analysis Plan for imputing missing or partially missing dates, if deemed appropriate, under specific data topics. Imputed or derived data will be flagged in the individual subject data listings. Imputed data will not be incorporated into any raw or primary datasets. The imputed data will be retained in the derived / analysis datasets.

The total duration for a subject *on-study* will be calculated as the difference between the date of initial study treatment in the *Induction Phase* and the last day of observation plus 1 day. All calculations for defining the duration on-study will follow the algorithm DURATION = [STUDY COMPLETION OR WITHDRAW DATE – INITIAL TREATMENT DATE + 1].

Summary statistics will consist of the count and percentage in each level for categorical variables, and the sample size (n) mean, median, standard deviation (SD), minimum, and maximum values for continuous variables. All mean and median values will be formatted to one more decimal place

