than the measured value. Standard deviation values will be formatted to two more decimal places than the measured value. Minimum and maximum values will be presented with the same number of decimal places as the measured value. The number and percentage of responses will be presented in the form XX (XX.X%). Pairwise differences between the treatment groups will be calculated and 95% confidence intervals constructed.

While no formal hypothesis testing is planned, probability values may be generated to determine the magnitude of the difference between subject groups for an endpoint. All p-values that round to 0.0000 will be presented as '<0.0001' and p-values that round to 1.0000 will be presented as '>0.9999'. P-values <0.05 will be discussed as being statistically significant.

All summary tables will include the analysis population sample size (i.e., number of subjects). Study Day 1 is defined as the day the subject receives their initial exposure to the active study device. All *study days* are determined relative to the day of initial treatment with the study device. Baseline values will be defined as those values recorded closest to, but prior to, the first active study treatment during the initial phase of the study. Date variables will be formatted as DDMMMYYYY for presentation. Where appropriate, only the measurements from the right foot will be used in the calculations.

D. Adverse Events

All summaries of adverse events will be based on treatment-emergent adverse events. Adverse events will be provided in a listing. The number and percentage of subjects experiencing adverse events will be summarized. Summaries by maximum severity and relationship to the study device (active or sham) will also be provided. Serious adverse events and adverse events leading to discontinuation from the study will be presented. Treatment-related adverse events will be defined as adverse events with investigator assessment of related or possibly related. In summaries of adverse events by severity and relationship to study device, patients reporting multiple episodes will be counted once under the worst severity and the strongest relationship, respectively. Serious adverse events will also be presented by relationship to treatment. The number of patients with at least one adverse event will be tabulated for each treatment group. The number of adverse events for each treatment group will also be tabulated.

E. Sample Size

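### The daily pain diary is not summarised: the only tabulation rule would base the secondary NPRS endpoint on one Day 120 (or last) rating, where a last-week diary mean would be more precise at almost no cost.

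*Combined protocol and SAP*

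**What the plan says.** - **Collection.** Appendix A, footnote 6: "Numeric pain scores along with weekly PGIC will be recorded by the subject on the diary each day immediately after the morning treatment". Appendix C, headed "SUBJECT DIARY FOR DAILY PAIN SCORE AND WEEKLY GLOBAL IMPRESSION OF CHANGE", tells the subject: "Circle the Pain Score which represents your average Pain over the last 24 hours after completing your Morning (am) treatment". Section III.J starts treatment on the morning of Day 1 and continues it to Day 120 for randomised subjects.
- **Endpoint.** The synopsis lists as secondary the "change in Pain Intensity using the 11-point Numeric Pain Rating Scale (NPRS) from baseline to end of treatment". It gives no derivation of the end value.
- **Tabulation.** Section VI.C: "The tabulations will be based on the paired results for the change from the baseline to study day 120 for patients who are randomized", with a separate table for the last observation. Baseline is fixed in the same section: "Baseline values will be defined as those values recorded closest to, but prior to, the first active study treatment". Group differences with 95% confidence intervals follow.
- **Clinic ratings.** Appendix A schedules a clinic NPRS at Screening, Enrollment and Day 61, and at Days 75 and 91 for non-responders. Nothing is marked at Day 105 or Day 121.
- **Everything else.** The synopsis sends all recorded data to listings. Section VI defers detail to a separate SAP and says that the methods in this section are its basis.

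**The concern.** The trial asks subjects for a rating every day, but its only tabulation rule needs a single end value. Because the clinic does not collect NPRS at Day 121, a Day 120 value can only come from the diary, and under VI.C it is one day's rating.

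Day-to-day variation in pain then passes undiluted into the active-sham difference. Subjects may also use as-needed analgesics freely (Section IV.N), so one day's rating can partly reflect that day's use. With at most 20 subjects per arm and no power claim, the 95% confidence interval is the main product of this endpoint, and its width is partly avoidable. If the day-120 requirement of the Completers set is applied endpoint by endpoint, one missed diary entry could also remove a subject's NPRS result despite a nearly full final week.

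**Working it through.** **Plan's own figure.** There is nothing to reproduce. Section VI.E gives 40 subjects as a convenience sample, with no effect size, SD or power.

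**How many ratings are used.** Diary days after randomisation, through Day 120:

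- randomised Day 61: 120 − 61 = 59
- randomised Day 75: 120 − 75 = 45
- randomised Day 91: 120 − 91 = 29

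The visit windows (+3 days) can reduce these to 56, 42 and 26. One rating is used in each case, so 25 to 58 are left over. Over the whole diary, one of about 120 enters (0.8%). A 7-rating window is available even to subjects randomised at Day 91.

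**Gain from a 7-day mean, keeping the single pre-treatment baseline.** All variance inputs are assumptions, since the documents give none: SD of true change sb = 1.5 or 2.0 points, day-to-day SD sw = 0.5, 1.0 or 1.5, and day-to-day autocorrelation 0 or 0.5 (first-order autoregressive).

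- Single end rating: Var = sb² + 2·sw²
- Mean of last 7: Var = sb² + sw²·(1 + f)
- f is the variance of a 7-day mean relative to one day. At autocorrelation 0, f = 1/7 = 0.143. At 0.5, f = (1/7)·[1 + 2·Σ(1 − k/7)·0.5^k, k = 1 to 6] = 2.433/7 = 0.348.
- Proportional cut = sw²·(1 − f) / (sb² + 2·sw²)

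| sb | sw | Cut, f = 0.143 | Cut, f = 0.348 |
|---|---|---|---|
| 1.5 | 0.5 | 7.8% | 5.9% |
| 1.5 | 1.0 | 20.2% | 15.3% |
| 1.5 | 1.5 | 28.6% | 21.7% |
| 2.0 | 0.5 | 4.8% | 3.6% |
| 2.0 | 1.0 | 14.3% | 10.9% |
| 2.0 | 1.5 | 22.7% | 17.3% |

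At the extremes:

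- Smallest: 0.25 × 0.652 / 4.5 = 3.6%. Interval width falls by 1 − √0.964 = 1.8%. Equivalent extra subjects: 1/0.964 − 1 = 3.8%.
- Largest: 2.25 × 0.857 / 6.75 = 28.6%. Interval width falls by 1 − √0.714 = 15.5%. Equivalent extra subjects: 1/0.714 − 1 = 40%.

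**Cross-check with another variance model.** Let s be the SD of one rating, rs the correlation between nearby days and rl the correlation between baseline and end of treatment (all assumed). With m end ratings, Var = s²·[1 + (1 + (m − 1)·rs)/m − 2·rl], and the 95% half-width is t·√(2·Var/n). With n = 20 per arm, s = 2.0, rl = 0.5 and t(38) = 2.024:

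| rs | Half-width, 1 rating | Half-width, 7-day mean | SE ratio |
|---|---|---|---|
| 0.5 | 1.28 | 0.97 | 0.76 |
| 0.7 | 1.28 | 1.10 | 0.86 |
| 0.9 | 1.28 | 1.22 | 0.96 |

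The SE falls by 4% to 24%. The upper end needs rs = rl, meaning that ratings on neighbouring days correlate no better than ratings four months apart. That is unlikely, so I rest on the first range. A 14-day window adds little (SE ratio 0.73 to 0.95).

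**The case against.** **The single-rating endpoint is inferred.** VI.C is a general rule that names neither NPRS nor the diary, and the separate SAP, which is not in the text reviewed, could define a diary average. This stands as a limit on wording: a reader might infer that the plan expressly chooses one rating, and it does not. But VI.C is declared to be the basis of that SAP and is the only rule given, so following the plan as written leads to one rating.

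**"Discarded" would be too strong.** A reader might infer that the remaining diary data are thrown away. They are listed, and nothing forbids summarising them. They simply have no planned summary.

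**NPRS is not the only pain measure after randomisation.** The BPI, which covers pain severity, is due at Day 121, and the weekly PGIC takes in pain reduction. The urgency is lower than the NPRS gap alone suggests.

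**A larger gain is tempting but unsupported.** A reader might expect much more from averaging at both ends. The diary starts after the first treatment, so the pre-treatment baseline cannot be averaged. Changing to a pre-randomisation reference would compare changes over two different periods, and no single assumed SD covers both.

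**One odd final day does not decide a subject's outcome.** The plan tabulates means and differences and has no end-of-study responder classification. The cost is noise, not misclassification.

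**Standing of the endpoint.** NPRS is one of several secondary endpoints in a proof-of-concept study without formal testing. This limits the weight of the point, but not the reason to make an inexpensive change.

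**Conclusion.** The point holds as an inexpensive gain in precision for a secondary endpoint. As written, VI.C brings one diary rating per randomised subject into the NPRS contrast, although 26 to 59 are due after randomisation. If ratings vary from day to day and neighbouring days are not perfectly correlated, a 7-day mean is more precise. The direction is therefore secure, but the size is not. On the assumed inputs the variance of the change falls by about 4% to 29% and the interval width by about 2% to 15%; the low end is negligible and the high end is worth having in arms of at most 20. The VPT and QST primary endpoints are unaffected.

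**What to change.** In Section VI.C, and carried into the SAP before unblinding:

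1. Define end-of-treatment NPRS as the mean of the last 7 available diary ratings made after randomisation on the assigned device. Pre-specify a minimum number (for example 4) and how a subject with fewer is handled. The same definition serves subjects who stop early.
2. Tabulate its change from the existing pre-treatment baseline, and the active-sham difference with 95% confidence interval.
3. As a supportive analysis, adjust that difference for the mean of the 7 diary ratings before randomisation. Subjects who kept the diary have these after at least 60 days of active treatment.
4. Keep the single Day 120 rating as a listing or sensitivity result.

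The cost is a paragraph of text, one derived variable and a small missing-data rule, with no new data collection. The drawback is that the endpoint then describes the last week rather than the last day. For a subject who stops soon after randomisation, the window covers early days on the assigned device. The 7-rating window and the minimum of 4 are judgements, not figures from the documents; what matters is fixing them in advance.
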